**Table 2 Schedule of Clinical Laboratory Samples and Estimated Blood Volume**

Clinical chemistry (including serum pregnancy test at Screening for females of childbearing potential): Screening; Baseline a ; Visits 3, 4, 5, and 6/Early Termination; and at the Safety Follow-up visit	7 × 3.5 mL	24.5 mL
Hematology: Screening; Baseline a ; Visits 3, 4, 5, and 6/Early Termination; and at the Safety Follow-up visit	7 × 2 mL	14 mL
Approximate total blood volume per subject		38.5 mL

a Required if the Baseline visit occurs outside of the screening window (i.e., >29 days after the Screening Visit).

## 6.10.2 Sample Collection, Storage, and Shipping

### 6.10.2.1 Clinical Laboratory Test Samples

The laboratory will supply detailed instructions and all containers for blood and urine investigations. Blood and urine sample volumes will meet the laboratory's specifications. The actual time of blood collection for all samples will be recorded.

Safety laboratory blood samples for hematology and serum chemistry tests will be collected at Screening; at Visits 3, 4, 5, and 6 or Early Termination; and at the Safety Follow-up visit. If the Baseline visit occurs outside of the screening window (i.e., >29 days after the Screening visit), hematology and chemistry tests should also be collected at the Baseline visit. Table 2 shows the schedule for collection of blood and the total estimated blood volume to be collected during the study.

A urine sample for urinalysis will be collected at Screening; at Visits 3, 4, 5, and 6 or Early Termination; and at the Safety Follow-up visit. A repeat urinalysis should be obtained if the Baseline visit occurs outside of the screening window (i.e., >29 days after the Screening visit). Samples obtained at other unscheduled visits at the investigator's discretion may be analyzed.

The urine sample taken at Screening will also be used for urine drug testing.

[figure not shown]
Alcohol breath tests will be performed at all study visits.

A serum pregnancy test for females of childbearing potential will be performed at Screening. Urine pregnancy tests will be performed at Baseline; at Visits, 3, 4, 5, and 6 or Early Termination; and at the Safety Follow-up visit (Table 1).

#### 6.10.2.2 Blood Samples for Pharmacokinetic Analysis

Subjects who enrolled in the study prior to Amendment 2 implementation would have participated in PK evaluation. Refer to Protocol Amendment 1 for the details regarding blood sample collection.

The bioanalysis will be performed by a central bioanalytical laboratory:

### 6.11 Dispensing Study Drug

Study drug will be dispensed to subjects at the Baseline/Randomization (Visit 2) and at Visits 3, 4, and 5 or at alternative intervals if necessary to comply with State and local laws and regulations. Subjects will be instructed to begin daily dosing with the new supply of study drug the day after the completion of Visits 2, 3, 4, and 5. Subjects will also be provided with dosing instructions consistent with the restrictions described in [Section 5.8](#). On Treatment Visits 3, 4, 5, and 6, dosing from the subject's drug supply will be observed and documented by site staff at the study center as described in [Section 7](#) and [Appendix 1](#).

### 6.12 Efficacy Assessments

#### 6.12.1 Epworth Sleepiness Scale

The ESS is a self-administered questionnaire with 8 questions asking the subject how likely they would be to doze off or fall asleep in different situations. Responses range from 0 = would never doze to 3 = high chance of dozing ([Appendix 13](#)). Subjects will be asked to complete the ESS with regard to the level of sleepiness they experienced over the past 7 days at Screening, Baseline; at Visits 3, 4, 5, and 6; and at the Safety Follow-up visit. The ESS provides a measure of a person's general level of sleepiness, or their average sleep propensity in daily life. It is a validated measure with high specificity and sensitivity for assessing subjective sleepiness ([Johns 1991](#); [Broderick et al. 2013](#)).

#### 6.12.2 Movement Disorder Society-Unified Parkinson's Disease Rating Scale – Parts III and IV

The Movement Disorder Society-sponsored revision of the Unified Parkinson's Disease Rating Scale (MDS-UPDRS) is a 4-part clinical rating scale for patients with Parkinson's disease. Part III measures motor function by examination and Hoehn and Yahr staging, and Part IV measures dyskinesias, motor fluctuations, and "off dystonia" ([Goetz et al. 2008](#); [Appendix 14](#)). Subjects will complete the MDS-UPDRS Parts III and IV at Baseline and at Visits 3, 4, 5, and 6.

### 6.12.3 Maintenance of Wakefulness Test

The MWT is the standard objective measure of an individual's ability to remain awake in a darkened, quiet environment and is commonly used to assess response to treatment (Doghramji et al. 1997, Mitler et al. 1982, AASM 2014). Only for subjects enrolled in Group 1, a 3-trial (with the option to do a fourth trial), 40-minute MWT will be performed at the Baseline visit and at Visits 3, 4, 5, and 6.

Each MWT during the study should be started at approximately the same time of the day. During the MWT trials, subjects should be seated in bed in a darkened room with the back and head supported by a bedrest (bolster pillow) such that their neck is not uncomfortably flexed or extended (Littner et al. 2005). Subjects will be instructed to sit still and remain awake for as long as possible during each of the three (or four) 40-minute trials separated by 2-hour intervals. The first MWT trial should occur approximately 1 hour after dosing with study drug at all visits at which the MWT will be conducted. If the subject falls asleep during a trial, they will be awakened and instructed to remain awake until the next trial. If the subject does not fall asleep, then the specific trial is terminated at 40 minutes and a sleep latency of 40 minutes is recorded. The subject is then instructed to remain awake (and will be awoken if they fall asleep) until the next trial.

Data from the MWT should be recorded and saved electronically, and any technician notes should also be maintained for potential transfer to Jazz Pharmaceuticals at the end of the study. A central reader will also evaluate all Baseline and Post-Baseline MWT trials for calculation of changes from Baseline.

Before the start of the first MWT on a given day, subjects will be asked the following question: "How long did you sleep last night?" This information should be recorded and may be used as a factor in the statistical analysis.

### 6.12.4 Clinician Global Impression of Severity

The CGIs is a 7-point Likert-type rating scale and a widely used assessment in clinical psychopharmacology trials to assess severity of illness (Appendix 15). The responses of this investigator-completed scale range from 1 = normal, no signs of illness to 7 = among the most extremely ill patients. The investigator will rate his/her impression of the severity of the subject's current condition at Baseline relative to his/her experience with this patient population.

### 6.12.5 Clinician Global Impression of Change

The CGIC is a 7-point Likert-type rating scale and a widely used assessment to assess efficacy in clinical drug trials (Appendix 16). Investigators will rate their impression of any change from baseline in the subject's condition on a 7-point scale ranging from 1 = very much improved to 7 = very much worse at Visits 3, 4, 5, and 6.

### 6.12.6 Patient Global Impression of Change

The PGIC is a 7-point Likert-type rating scale and a widely used assessment to assess efficacy in clinical drug trials ([Appendix 17](#)). Subjects will rate the change from baseline in their condition on a 7-point scale ranging from 1 = very much improved to 7 = very much worse at Visits 3, 4, 5, and 6.

### 6.12.7 Apathy Scale

The Apathy Scale assesses apathy in patients with PD ([Starkstein et al. 1992](#)) ([Appendix 18](#)). The maximum total score possible is 42, with higher scores indicating more severe apathy. Subjects will complete the Apathy Scale at Baseline and at Visits 3, 4, 5, and 6.

### 6.12.8 Fatigue Severity Scale

The FSS, a 7-point Likert-type rating scale, is the most commonly used fatigue scale across all conditions and is recommended by the Movement Disorders Society Task Force for both fatigue screening and severity ratings in Parkinson's disease ([Friedman et al. 2010](#); [Krupp et al. 1989](#)) ([Appendix 19](#)). The scale consists of 9 items and the total score represents the mean score of each of the 9 items, yielding a score range between 1 and 7, with higher scores indicating a higher level of fatigue. Subjects will complete the FSS at Baseline and at Visits 3, 4, 5, and 6.

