## **16.1. KEY EFFICACY ENDPOINT**

### **16.1.1. KEY EFFICACY ENDPOINT & DERIVATION**

The key efficacy endpoint is defined in terms of change from study Baseline to the end of treatment period.

The ESS is a self-administered questionnaire with 8 questions asking the subject how likely they would be to doze off or fall asleep in different situations. Responses range from “0 = would never doze” to “3 = high chance of dozing”. Subjects will be asked to complete the ESS with regard to the level of sleepiness they experienced over the past 7 days at Screening, Baseline, Visits 3, 4, 5, and 6, and at the Safety Follow-up visit. The ESS provides a measure of a person’s general level of sleepiness, or their average sleep propensity in daily life. It is a validated measure with high specificity and sensitivity for assessing subjective sleepiness.

The ESS total score is the sum of the 8 individual question scores. If three or more question scores are missing at a specific time point, the ESS total score will be set to missing. If one or two ESS question scores are missing at a specific time point, the mean of the remaining seven or six non-missing ESS question scores at that time point will be used to impute the missing ESS item scores. The ESS total score will be then calculated as the sum of the observed and imputed item scores.

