#### **16.2.1.2. MDS-UPDRS PARTS III AND IV SCORES**

Movement Disorder Society-sponsored revision of the Unified Parkinson's Disease Rating Scale (MDS-UPDRS) is a 4-part clinical rating scale for patients with Parkinson's disease. Part III measures motor function by examination and Hoehn and Yahr staging, and Part IV measures dyskinesias, motor fluctuations, and "off dystonia". Subjects will complete the MDS-UPDRS Parts III and IV at Baseline and at Visits 3, 4, 5, and 6.

The following endpoints will be summarized:

- Observed and change from Baseline in MDS-UPDRS Part III total score, where the total score is the sum of all individual scores for the 33 items. If the scores of 8 or more items are missing, then the MDS-UPDRS Part III total score is not evaluable and will be set to missing. If the score of 7 or fewer items are missing, the MDS-UPDRS Part III total score will be equal to the mean of the non-missing scores multiplies by 33 and then, rounded to the integer (Goetz et al. 2015);
- Observed and change from Baseline in MDS-UPDRS Part IV total score, where the total score is the sum of all individual scores for items 4.1 to 4.6. If the score of 1 item is missing, then the MDS-UPDRS Part IV total score is not evaluable and will be set to missing (Goetz et al. 2015);
- Observed and change from Baseline in MDS-UPDRS Part IV *Dyskinesias* subcomponent score, where the subcomponent score is the sum of all individual scores for items 4.1 to 4.2. If the score of 1 item is missing, then the MDS-UPDRS Part IV *Dyskinesias* subcomponent score is not evaluable and will be set to missing (Goetz et al. 2015);
- Observed and change from Baseline in MDS-UPDRS Part IV *Motor fluctuations* subcomponent score, where the subcomponent score is the sum of all individual scores for items 4.3 to 4.5. If the score of 1 item is missing, then the MDS-UPDRS Part IV *Motor fluctuations* subcomponent score is not evaluable and will be set to missing (Goetz et al. 2015);
- Observed and change from Baseline in MDS-UPDRS Part IV *"Off" dystonia* subcomponent score, where the subcomponent score is individual score for item 4.6.

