### 16.2.1.5. FSS

The Fatigue Severity Scale (FSS), a 7-point Likert-type rating scale. The scale consists of 9 items; the total score represents the mean score of each of the 9 items, yielding a score range between 1 and 7, with higher scores indicating a higher level of fatigue. If the score of 1 item is missing, then the FSS total score will be set to missing. Subjects will complete the FSS at Baseline and at Visits 3, 4, 5, and 6.

The observed and change from Baseline in FSS total score to the end of period will be summarized.

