### 16.2.1.6. APATHY SCALE

The Apathy Scale assesses apathy in patients with PD and consists of 14 questions with four possible answers: items 1 to 8: Not at All (3), Slight (2), Some (1), A Lot (0); items 9 to 14: Not at All (0), Slight (1), Some (2), A Lot (3). The total score, ranging from 0 to 42, is obtained by summing the scores of the 14 items, with higher scores indicating more severe apathy. If the score of 1 question is missing, then the Apathy total score will be set to missing. Subjects will complete the Apathy Scale at Baseline and at Visits 3, 4, 5, and 6.

The following endpoints will be summarized:

- Observed and change from Baseline in Apathy total score
- Observed and change from Baseline in the first Apathy subscale score (i.e., cognitive-behavioral aspects of apathy, obtained by summing items 1, 2, and 4 to 8). If the score of 1 question is

missing, then the subscale score will be set to missing.

- Observed and change from Baseline in the second Apathy subscale score (i.e., general apathy, obtained by summing items 3, and 9 to 14). If the score of 1 question is missing, then the subscale score will be set to missing.

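### One missing item voids the FSS or Apathy total, although the SAP prorates ESS and MDS-UPDRS Part III; tolerating one or two missing items would be a cheap, low-priority improvement

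*Protocol*

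**What the plan says.** **FSS.** Protocol 6.12.8 gives the definition: "The scale consists of 9 items and the total score represents the mean score of each of the 9 items". SAP 16.2.1.5 keeps it and adds: "If the score of 1 item is missing, then the FSS total score will be set to missing".

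**Apathy Scale.** SAP 16.2.1.6 describes an instrument that "consists of 14 questions with four possible answers", summed to a total of 0 to 42, with the rule: "If the score of 1 question is missing, then the Apathy total score will be set to missing". Each of its two seven-item subscales has the same rule.

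**Scales that are prorated.** For ESS (SAP 16.1.1), with one or two of eight items missing, "the mean of the remaining seven or six non-missing ESS question scores at that time point will be used to impute" the gaps. For MDS-UPDRS Part III (SAP 16.2.1.2), with up to seven of 33 items missing, "the MDS-UPDRS Part III total score will be equal to the mean of the non-missing scores multiplies by 33", then rounded.

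**Other strict scales.** For MDS-UPDRS Part IV: "If the score of 1 item is missing, then the MDS-UPDRS Part IV total score is not evaluable and will be set to missing". SCOPA-cog (SAP 16.2.1.7) is also strict.

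**General rules.** Protocol 9.6 rules out imputation. SAP 7.2 names ESS and Part III as the only score-level exceptions, and SAP 3.6 lists both as changes from the protocol. SAP 16.2.2 rules out imputation of missing exploratory endpoints. SAP 16.2.3.3 analyses FSS and Apathy with the ESS mixed model of SAP 16.1.4: change from Baseline as outcome, Baseline as covariate.

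**The concern.** An FSS form with eight of nine answers, or an Apathy form with 13 of 14, contributes nothing to the analysis of its total. The items within each scale share one range (1 to 7 for FSS, 0 to 3 for Apathy after scoring), and the FSS total is already an average. Prorating therefore keeps both totals on their own scale. The SAP accepts that approach for two other scales and gives no reason for refusing it here.

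Baseline matters most. Both scales are scheduled only once before dosing, and Baseline enters both the outcome and the covariate. A void Baseline total therefore leaves that subject with no usable record in that score's change model at any of Visits 3 to 6. A void total at a later visit costs that period only.

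Fatigue and apathy are two of the three nonmotor symptoms named in the exploratory objective, and the trial aims for about 40 completers. What is at stake is precision on those two scores, and possibly some selection. The FSS form (Protocol Appendix 19) asks about exercise and work. Unlike the ESS form (Appendix 13), it does not tell subjects to answer every question even where a situation has not arisen.

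**Working it through.** **Plan's own figure.** There is none for FSS or Apathy. The only sample-size figure is for ESS: 80% power with 34 completers, difference 3, SD 6, two-sided 0.05. With 6 read as the SD of the within-subject difference, the noncentral t calculation (32 df) gives 80.7%, so it reproduces. It says nothing about skipped items.

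**Inputs.** Items per form: n = 9 (FSS, Protocol 6.12.8) and n = 14 (Apathy, SAP 16.2.1.6). Randomised: 49 (Protocol 9.3). The chance p that an item is skipped is not in the documents. I assume 0.5%, 1% and 2%, with items independent within a form.

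**Tolerance elsewhere in the SAP.** ESS 2/8 = 25%; Part III 7/33 = 21%; FSS and Apathy 0%.

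**Step 1. One form voided under the SAP rule:** v = 1 − (1 − p)^n. For FSS at 1%: 1 − 0.99^9 = 8.6%.

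**Step 2. Change score lost.** A change score needs complete forms at both Baseline and the visit. Two cases across visits:
- the same subjects skip every time: loss = v, falling on whole subjects;
- skips independent between visits: loss = 1 − (1 − v)² = 1 − (1 − p)^(2n). For FSS at 1%: 1 − 0.99^18 = 16.5%.

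| p | FSS, same subjects | FSS, independent | Apathy, same subjects | Apathy, independent |
|---|---|---|---|---|
| 0.5% | 4.4% | 8.6% | 6.8% | 13.1% |
| 1% | 8.6% | 16.5% | 13.1% | 24.5% |
| 2% | 16.6% | 30.5% | 24.6% | 43.2% |

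The expected number of void Baselines is 49 × v. At p = 1% this is 4.2 subjects for FSS and 6.4 for Apathy.

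**Step 3. Loss if one or two missing items are tolerated.** A form is void only with three or more missing: t = 1 − Σ C(n,k) p^k (1 − p)^(n−k), summed over k = 0, 1, 2. With independent visits the change-score loss is 1 − (1 − t)².

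| p | FSS t | FSS change lost | Apathy t | Apathy change lost |
|---|---|---|---|---|
| 0.5% | 0.001% | 0.002% | 0.004% | 0.009% |
| 1% | 0.008% | 0.016% | 0.034% | 0.067% |
| 2% | 0.061% | 0.12% | 0.25% | 0.49% |

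**Step 4. Largest error that prorating can introduce.** Let m be the mean of the answered items and x the unseen answer. With one FSS item missing, the prorated total differs from the full one by (m − x)/9, at most 6/9 = 0.67 on the 1 to 7 scale. With one Apathy item missing, it differs by m − x, at most 3 points of 42. With two missing, these limits double.

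**Limit of the calculation.** If skips cluster within a form (a few subjects leave many items blank), strict-rule losses are smaller than shown and prorating recovers less. The same-subjects columns are therefore not a lower bound.

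**The case against.** The strongest reply is that the strict rule is the SAP's default. Protocol 9.6 forbids imputation, SAP 7.2 makes only two exceptions, and Part IV and SCOPA-cog are treated as FSS and Apathy are. ESS is the key endpoint, and the Part III rule cites a published source. On this view, asking for two more exceptions is a preference. That largely stands. A reader might infer that the strict rule contradicts the protocol, or that the FSS definition in Protocol 6.12.8 is faulty. The documents support neither: an average of nine items is compatible with requiring all nine.

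What remains is an uneven standard without a stated reason. Part IV cites a source for its strict rule. SCOPA-cog items have different maxima, and its Screening score could serve as Baseline. Neither consideration applies to FSS or Apathy.

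Four further points stand as limits:
- Protocol section 7 allows a failed or incorrectly conducted assessment to be repeated with sponsor permission, and SAP 6.2 accepts a pre-dose retest as Baseline. A void Baseline can be rescued, but no repeat is scheduled.
- An examiner reads out the Apathy questions (Protocol Appendix 18), so its skip rate is probably at the low end.
- SAP 16.2.3.3 tabulates missing scores by visit and treatment, so any loss will be visible, though not recovered.
- One missing Apathy item leaves the other subscale intact.

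**Conclusion.** The point holds as a cheap improvement to two exploratory endpoints. It does not identify an error in the plan. Under the SAP rule, skip rates of 0.5% to 2% would cost 4.4% to 30.5% of FSS change scores and 6.8% to 43.2% of Apathy change scores, depending on the rate and on whether skips recur in the same subjects. These figures rest on assumed rates and on independence of items within a form. The upper ends also need independence between visits, which does not fit subjects who keep skipping an item that does not apply to them; for those, the same-subjects columns are the relevant ones.

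Two stronger readings are tempting and not supported. One is that a single skipped item drops a subject from the efficacy analysis. SAP 5.2 excludes the subject from that endpoint only, and observed values at visits with complete forms are still summarised. The other is that the loss is known to be selective. Selection is plausible for FSS, but nothing in the documents shows it, and the exercise and work items have no counterpart on the Apathy form. The primary safety objective and ESS are unaffected.

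**What to change.** Before unblinding, amend SAP 16.2.1.5 and 16.2.1.6:
- With one or two items missing, FSS total = mean of the answered items.
- With one or two items missing, Apathy total = mean of the answered items × 14, after reverse scoring items 1 to 8.
- With three or more missing, set the total to missing.
- State whether the seven-item Apathy subscales stay strict or are prorated in proportion (2 of 14 corresponds to 1 of 7), so that a prorated total beside a missing subscale is intended.
- Keep the complete-item score as a sensitivity analysis.
- Add both scales to the exceptions in SAP 7.2 and to the changes listed in SAP 3.6.

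SCOPA-cog can stay as it is because its items have different maxima. Two of nine (22%) and two of 14 (14%) are both within the 25% already accepted for ESS.

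The cost is a few sentences and minor programming. The downside is the assumption that a skipped item resembles the subject's other answers, which the SAP already makes for ESS and Part III. The amendment also moves two more scores away from Protocol 9.6, which is why SAP 3.6 must record it.

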### 6.12.9 Scales for Outcomes of Parkinson's Disease-Cognition

The SCOPA-cog evaluates the specific cognitive deficits in PD ([Marinus et al. 2003](#)) ([Appendix 20](#)). The scale consists of 10 items with a total possible score of 43, with higher scores indicative of better cognition. Subjects will complete the SCOPA-cog at the Screening, Baseline, and at Visits 3, 4, 5, and 6.

## 6.13 Pharmacokinetic Assessments

### 6.13.1 Blood Samples

Subjects who enrolled in the study prior to Amendment 2 implementation would have participated in PK evaluation. Refer to Protocol Amendment 1 for the details regarding blood sample collection.

### 6.13.2 Pharmacokinetic Parameters

Plasma PK parameters to be calculated for JZP-110 concentrations will include, but may not be limited to, the following, as appropriate:

AUC 0-t	Area under the plasma concentration versus time curve from time 0 to t hours, the last detectable concentration, calculated by means of the trapezoidal rule
AUC 0-inf	Area under the plasma concentration versus time curve from time 0 to infinity, calculated as $AUC = AUC_{0-t} + C_t / K_{el}$ , where $C_t$ is concentration at time t, and $K_{el}$ is the elimination rate constant estimated from the fitted terminal elimination phase (see $K_{el}$ )
$C_{max}$	Maximum plasma drug concentration
$T_{max}$	Time to reach $C_{max}$
$t_{1/2}$	Apparent terminal elimination half-life, calculated as $\ln(2) / K_{el}$
$K_{el}$	Apparent elimination rate constant estimated by unweighted log-linear regression of the last portion of the plasma concentration profile. This log-linear regression will be fitted according to the least-squares approach. Starting with the last 3 quantifiable measurements and stepping back, the best fit will be determined by minimizing the residual sums of squares; the time interval and the number of time points used for this optimal fit will be provided.
CL/F	Apparent oral clearance (calculated as Dose/AUC inf )
Vd/F	Apparent oral volume of distribution (calculated as oral clearance/ $K_{el}$ )

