### 1.3.1 Clinical Pharmacokinetics and Product Metabolism

JZP-110 is eliminated primarily via the renal route, with at least 90% of the dose being excreted as unchanged drug within 48 hours. Following single dosing and repeated doses administered twice daily, JZP-110 exposure was dose-proportional, absorption (time to maximum plasma concentration [ $t_{max}$ ]: 1.3 to 3.0 hours) and elimination ( $t_{1/2}$ : 5 to 7.6 hours) were relatively rapid, and steady state was reached in 3 days. JZP-110 displayed linear PK during 14 days of dosing over the dose range of 200 to 1000 mg per day. Limited accumulation and no enzyme auto-induction were evident.

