day and undergo assessments for efficacy, safety, and tolerability (Visits 3, 4, 5, and 6). Subjects will take their study drug with water in the morning at the study clinic after predose assessments are completed. Subjects may be served a light meal at 15 minutes after dosing. Pending the investigator's assessment of safety and tolerability, subjects will proceed to the next treatment period. Subjects will receive their last dose of study drug at Visit 6 (Day 28) prior to the Week 4 visit assessments. Subjects will return for a Safety Follow-up visit (Visit 7) approximately 7 days after the last dose of study drug for follow-up safety assessments. Unless there are outstanding safety issues that require additional follow-up, subjects will be discharged from the study at the Safety Follow-up visit (Visit 7).

[figure not shown]
Safety and tolerability will be assessed throughout the study and will include the following: monitoring of AEs, discontinuations due to AEs, changes in physical examination findings, ECGs, clinical laboratory tests, vital sign measurements (including measuring seated and standing blood pressure), and change in response to the Columbia-Suicide Severity Rating Scale (C-SSRS) at each visit.

Efficacy will be assessed by the change from baseline in the ESS score, and for subjects who enroll in Group 1 and subjects who enrolled prior to Amendment 2, by the change from baseline in mean sleep latency time as objectively measured using either 3 or 4 trials of the MWT.

Exploratory efficacy assessments will include changes in scores from baseline and/or the percentages of subjects improved, as applicable, on the CGIc, PGIf, Fatigue Severity Scale (FSS), Apathy Scale, and the Scales for Outcomes in Parkinson's disease-cognition (SCOPA-cog).

Parkinson's disease clinical status (e.g., motor fluctuations, dyskinesia) will be assessed using the Movement Disorders Society-Unified Parkinson's Disease Rating Scale (MDS-UPDRS) Parts III and IV.

In addition, subjects who enrolled in the study prior to Amendment 2 implementation would have participated in the PK evaluation. Blood samples for PK analysis were to be collected from each subject at predose and at 1, 2, 3, 4, 5, and 6 hours after dosing at Visits 3, 4, 5, and 6. A sample was also collected 7 to 8 hours after dosing, as feasible, at each study center visit.

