## 18.3. PHARMACOKINETIC PARAMETERS

For PK parameter calculations, pre-dose samples that are BLQ or missing will be assigned a numerical value of zero. Any other BLQ concentrations will be assigned a value of zero if they precede quantifiable samples in the initial portion of the profile. A BLQ value that occurs between quantifiable data points, especially prior to  $C_{max}$ , will be evaluated to determine if an assigned concentration of zero makes sense, or if exclusion of the data (flagged out and treated as missing) is warranted. Following  $C_{max}$ , BLQ values embedded between 2 quantifiable data points will be treated as missing when calculating PK parameters. If a BLQ value occurs at the end of the collection interval (after the last quantifiable concentration), it will be set to zero. If consecutive BLQ concentrations are followed by quantifiable concentrations in the terminal portion of the concentration curve, these quantified values will be excluded from the PK analysis by setting them to missing, unless otherwise warranted by the concentration-time profile. Actual elapsed time from dosing on active treatment visits will be used for PK parameter calculations.

Plasma PK parameters to be calculated for JZP-110 concentrations by non-compartmental methods will include, but may not be limited to the following, as appropriate:

AUC 0-t,ss	Area under the plasma concentration-time curve from time zero (pre-dose) to time of last quantifiable concentration at time t, calculated by the Linear trapezoidal / Linear Interpolation summation method.
-----------------------	--

$C_{max,ss}$	Maximum plasma concentration, obtained directly from the observed concentration versus time data.
$t_{max,ss}$	Time of maximum plasma concentration, obtained directly from the observed concentration versus time data.
$t_{1/2}$	Apparent terminal elimination half-life, determined as $\ln(2)/K_{el}$ .
$K_{el}$	Apparent terminal elimination rate constant estimated by unweighted log-linear regression of the last portion of the plasma concentration profile.
$AUC_{0-tau}$	Area under the plasma concentration-time curve from time zero (pre-dose) through the dosing interval. Given the 24 hour dosing interval and blood collections for PK available through 8 hours, the estimated value will reflect an extrapolation and should be considered with caution.
$CL/F_{ss}$	Apparent oral systemic clearance, calculated as $Dose/AUC_{0-tau}$ .

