$Vd/F_{ss}$	Apparent oral volume of distribution, calculated as $Dose/K_{el} \times AUC_{0-tau}$ .

In addition, dose normalized  $AUC_{0-t,ss}$  and  $C_{max,ss}$  may be reported.

The following PK parameters will be calculated for diagnostic purposes and listed, but will not be summarized.

[figure not shown]
$t_{1/2}$ , Interval	The time interval (h) of the log-linear regression to determine $K_{el}$ .
$t_{1/2}$ , N	Number of data points included in the least squares log-linear regression analysis to determine $K_{el}$ . A minimum of the last 3 quantifiable data points excluding $t_{max,ss}$ will be used for determination.
Rsq	Goodness-of-fit statistic for calculation of $K_{el}$ (Regression coefficient).

Pharmacokinetic parameters will be summarized by treatment using descriptive statistics. Geometric mean will not be calculated for  $t_{max}$ . A subject listing of individual PK parameters for each treatment will be provided. For  $t_{max}$  a frequency table will also be provided.

Scatter plots of individual and mean PK parameters versus treatment will be presented. Additionally, graphical presentations of PK data may be added at the discretion of the PK scientists, if further illustration of the PK results is deemed appropriate.

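### The protocol's rule for choosing the Kel fit can only return the last 3 points, and SAP 18.3 leaves the rule out without stating another

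*Protocol*

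**What the plan says.** Protocol 6.13.2 defines Kel as follows: "Apparent elimination rate constant estimated by unweighted log-linear regression of the last portion of the plasma concentration profile". It then gives the selection rule, "Starting with the last 3 quantifiable measurements and stepping back, the best fit will be determined by minimizing the residual sums of squares", and promises that "the time interval and the number of time points used for this optimal fit will be provided". No adjustment for the number of points is mentioned. In the same section Kel feeds the half-life, AUC0-inf, CL/F and Vd/F.

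SAP 18.3 again has Kel "estimated by unweighted log-linear regression of the last portion of the plasma concentration profile", but without the residual-sum-of-squares sentence. It requires at least the last 3 quantifiable points, not counting tmax,ss. For each fit it lists the interval, Rsq and the "Number of data points included in the least squares log-linear regression analysis", all described as diagnostic. Clearance and volume now use AUC0-tau, extrapolated to 24 h. SAP 3.6 records that the non-compartmental analysis is now on a multiple-dose basis under 18.3 and says nothing about how the number of points is chosen.

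Blood for PK was "collected from each subject at predose and at 1, 2, 3, 4, 5, and 6 hours after dosing" (Protocol 3.1), and further: "A sample was also collected 7 to 8 hours after dosing, as feasible, at each study center visit".

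**The concern.** The protocol sentence describes a search over 3, 4, 5 or more points and promises to report how many were used, so its authors evidently expected the number to vary. Under the stated criterion it cannot. Taken literally, the half-life and everything built on Kel would rest on three samples a few hours apart, and some profiles would give a flat or rising line and no half-life. If the SAP is read as having dropped the rule, the choice falls to the analyst or to a software default that neither document names. Characterising the PK is a secondary objective, and only subjects enrolled before Amendment 2 were sampled, so precision lost here cannot be regained by collecting more samples.

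**Working it through.** **Inputs.** Sampling times are from Protocol 3.1. The half-life of 5 to 7.6 h and the time to peak of 1.3 to 3.0 h are from Protocol 1.3.1. The documents give no assay or within-profile error, so 5% and 10% on the log-concentration scale are assumed. The plan states no precision figure to reproduce.

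**Step 1: what the criterion selects.** Let RSS(n) be the residual sum of squares of the line through the last n points. Adding one earlier point gives

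RSS(n+1) = RSS(n) + e²/(1 + h),

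where e is the error of the n-point line in predicting the new point and h ≥ 0 is that point's leverage term. The added quantity is never negative, so the minimum is at n = 3. A tie needs an earlier point lying exactly on the line. A numerical check on 20,000 arbitrary 7-point profiles chose 3 points in all 20,000. So did every simulated concentration profile in 24 scenarios. This result does not depend on the assumed error.

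**Step 2: the span.**
- Samples at 4, 5, 6 h or at 5, 6, 7 h: 2 h.
- Samples at 5, 6, 8 h: 3 h.
- Smallest share of a half-life: 2/7.6 = 0.26. Largest: 3/5 = 0.60.
- If the 6 h sample is missing, the last three are 4, 5 and 7 to 8 h, a span of 3 to 4 h.

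**Step 3: precision of a 3-point fit.** Kel = ln 2 / half-life, which is 0.1386 per h at 5 h and 0.0912 per h at 7.6 h. For a straight log-linear decline, CV(Kel) = σ / (Kel × √Sxx), where Sxx is the sum of squared deviations of the sampling times.

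| Points (h) | Sxx | 5 h, 5% | 7.6 h, 5% | 5 h, 10% | 7.6 h, 10% |
|---|---|---|---|---|---|
| 4, 5, 6 or 5, 6, 7 | 2 | 26% | 39% | 51% | 78% |
| 5, 6, 7.5 | 3.17 | 20% | 31% | 41% | 62% |
| 5, 6, 8 | 4.67 | 17% | 25% | 33% | 51% |

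The chance of a non-positive slope is Φ(−1/CV). In the worst cell, Φ(−1/0.775) = Φ(−1.29), about 10%.

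**Step 4: what adjusted R-squared would change.** Adjusted R-squared is 1 − (1 − R²)(n − 1)/(n − 2), which allows for n. The two rules were compared by simulation with the last sample at 6 or 7.5 h. Decline was either mono-exponential or followed first-order absorption at steady state with the observed tmax excluded; the absorption rates, down to 0.8 per h, are assumptions.
- Root mean squared error (RMSE) of Kel, bias included: about 17% to 76% with adjusted R-squared, against 20% to 78% with 3 points.
- With absorption modelled, adjusted R-squared was equal or better in all but one scenario (33% against 32%).
- Non-positive slopes at half-life 7.6 h, 10% error, samples to 6 h and mono-exponential decline: about 4% against 10%.

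**Step 5: what depends on Kel.** Under mono-exponential decline, the share of AUC0-tau beyond the last sample at time T is (exp(−Kel·T) − exp(−24·Kel)) / (1 − exp(−24·Kel)).
- T = 8 h, half-life 5 h: (0.330 − 0.036)/0.964 = 0.30.
- T = 6 h, half-life 7.6 h: (0.579 − 0.112)/0.888 = 0.53.

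So the choice of Kel fit also reaches AUC0-tau and CL/F, as well as half-life and Vd/F.

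**The case against.** The strongest reply is that the protocol sentence may no longer govern. SAP 3.6 points the non-compartmental analysis to 18.3, and 18.3 redefines Kel without the sentence and treats 3 points as a floor. That stands. A reader might infer that the reported half-lives will rest on 3 points in every subject; the documents do not support that, because the analysis under the SAP could use more. The reply does not supply a rule, however. Rsq is listed as a diagnostic, not as a selector.

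A reader might also infer that a better rule would cut the CV of Kel to 8–25% at 5% error, or 16–49% at 10%. Those figures come from fitting all post-peak points under a purely mono-exponential decline. They do not describe adjusted R-squared, which still picked 3 points in 27–36% of such profiles. With slow absorption (assumed 0.8 per h), fitting all points underestimated Kel by roughly 18–43%.

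Nor does every subject lose usable samples. With tmax at 3 h and no sample at 7 to 8 h, only 4, 5 and 6 h remain, and any rule with a 3-point minimum gives the same fit.

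It is fair to say that sampling to 6–8 h limits Kel under any rule. The SAP already advises caution on AUC0-tau and lists the interval and number of points for each fit. If a residual mean square, RSS/(n − 2), was meant, the number of points would vary, but the text does not say so.

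**Conclusion.** The concern holds as a defect in a stated rule, with small consequences. The protocol criterion defeats its own purpose whatever the error level, and the SAP neither repeats it, expressly withdraws it nor replaces it. The precision figures rest on assumed errors and absorption rates, and they show a modest improvement rather than a cure. The effect is confined to descriptive PK: Kel, half-life, extrapolated AUC, CL/F and Vd/F. Cmax, tmax, AUC0-t, the ESS analysis and safety do not use Kel. Low priority, but worth settling before the PK parameters are calculated.

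**What to change.** In SAP 18.3:
- State that the section supersedes the residual-sum-of-squares criterion in Protocol 6.13.2, and record this in SAP 3.6.
- Choose the number of points after tmax,ss (minimum 3) by the largest adjusted R-squared. Take the fit with more points when values lie within a stated tolerance, for example 0.0001.
- List the span of each fit in half-lives beside the interval and number of points already planned.
- Exclude fits with a non-positive slope from the summaries of half-life, AUC0-tau, CL/F and Vd/F, and report how many were excluded.

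The cost is a few lines of SAP text and a software setting. The downside is some bias in Kel in certain profiles, small beside the random error and already counted in the RMSE figures above.
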